5.9.4. Other Safety Parameters

5.9.4.1. Suicidal Ideation and Behavior

The Columbia-Suicide Severity Rating Scale (C-SSRS) will be used as a screening tool to prospectively evaluate suicidal ideation and behavior in this study, as part of a comprehensive evaluation of safety. The C-SSRS is an investigator-administered questionnaire^{15, 16} that defines five subtypes of suicidal ideation and 4 possible suicidal behaviors, as well as non-suicidal self-injurious behavior and completed suicide.

The maintenance baseline is defined as the most severe/maximum score at Week M-0. Suicidal ideation and behavior will be analyzed by the most severe/maximum post-maintenance baseline C-SSRS outcome or AE of suicidal ideation and behavior. Listings based on the **All Treated Analysis Set** will be provided for participants with positive (i.e., score >0) ideation and behavior.

5.10. Other Analyses

5.10.1. Pharmacokinetics

5.10.1.1. Serum Guselkumab Concentrations

PK analyses will be performed based on the **PK Analysis Set** and **Randomized PK Analysis Set** (Section 4), unless otherwise specified.

Descriptive statistics (N, mean, SD, median, range, coefficient of variation (%) and interquartile range) will be used to summarize concentrations at each sampling time point by treatment group (unless otherwise specified, the treatment group mentioned in this section refers to the maintenance treatment group). PK data may be displayed graphically over time by treatment group.

The proportion of participants without detectable serum guselkumab concentration (below the lower limit of quantification) at each visit by treatment group through Week M-44 will also be presented.

In addition, serum guselkumab concentrations at each visit based on **Randomized PK Analysis Set** will be presented:

- by induction and maintenance treatment groups
- by induction baseline body weight quartiles and maintenance treatment groups.

- Statistical Analysis Plan CNTO1959UCO3001 Amendment 2
- by induction baseline use of concomitant immunomodulators and maintenance treatment groups
- by induction baseline ADT failure status (Yes/No) and maintenance treatment groups

PK data will be displayed graphically, i.e.:

- Plot of median serum guselkumab concentrations by treatment group through Week M-44
- Plot of median serum guselkumab concentrations through Week M-44 by treatment group and Week M-44 clinical response status for the **Randomized PK Analysis Set**

Serum guselkumab concentrations will also be summarized for participants who had a dose adjustment and receive an increased dose (i.e., participants randomized to placebo and increased to guselkumab 200 mg, and participants randomized to guselkumab 100 mg and increased to 200 mg). Serum guselkumab concentrations over time will be summarized (when the number of participants permitted) starting from the time of dose adjustment. Summary of PK concentrations (micrograms/mL) through Week M-44; treated subjects who were randomized and did not have a dose increase will also be provided.

Data Handling Rules:

Unless otherwise specified, the following data handling rules will apply to PK analyses:

- Participants will be analyzed according to their assigned treatment.
- All serum concentration summaries for a particular time point will include data obtained from treated participants at the timepoint of interest without imputing any missing data.
- A concentration not quantifiable (below the lower limit of quantification) will be treated as 0 in the summary statistics and shown as the lower limit of quantification (< LLOQ) in the data listings.
- The data from a participant who meets any of the following dosing deviation criteria will be excluded from the by-visit data analyses from that point onwards:
 - Discontinued guselkumab administrations.
 - Skipped a guselkumab administration.
 - Received an incomplete / incorrect dose.
 - Received an incorrect study intervention.
 - Received an additional guselkumab dose.

In addition, if a participant has an administration outside of dosing windows (\pm 10 days), the concentration data collected at and after that visit will be excluded from the by-visit data analyses. For participants who received an increased dose at the time of dose adjustment, data after dose adjustment were excluded (this does not apply to the summary of serum guselkumab concentrations for participants who have a dose adjustment and receive an increased dose).

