for mirikizumab 200 mg SC q4w in the Phase 2 UC study supports this selection. In this Phase 2 UC study, a dose-response in maintenance efficacy was shown with the mirikizumab 200 mg SC q4w and 200 mg SC q12w dose regimens (Geert 2019). Among participants who achieved a clinical response to mirikizumab induction treatment at Week 12, the 200 mg SC q4w and 200 mg SC q12w regimens resulted in 47% and 37% of participants in remission at Week 52, respectively. In addition, among those in clinical remission at Week 12, 61% (200 mg q4w) and 39% (200 mg q12w) remained in clinical remission at Week 52. These data demonstrate that higher efficacy was observed based on key endpoints with the 200 mg SC q4w regimen relative to 200 mg SC q12w.

Of note, the maintenance dose regimens selected for this UC program are the same as those that are being evaluated in the ongoing guselkumab Phase 2/3 Crohn's disease study (guselkumab NCT03466411). Overall, the 2 guselkumab maintenance dose regimens (ie, 200 mg SC q4w and 100 mg SC q8w) would provide an approximately 4-fold dose range for the dose/exposure-response assessment of maintenance therapy in the treatment of UC.

With respect to safety of the maintenance dose regimens, and as shown in Table 4, the predicted exposure margins for the highest SC dose (200 mg q4w) relative to the NOAEL of 50 mg/kg/week in cynomolgus monkeys are approximately 33 to 40, which is considered adequate to support the long-term SC dosing (for chronic maintenance) in the guselkumab UC clinical development programs. Guselkumab is approved for the treatment of plaque psoriasis with a good long-term clinical safety profile (with data generated primarily at 100 mg SC q8w), and dose regimens as high as 200 mg SC q8w have been shown to have favorable safety in a 6 month Phase 2 trial in rheumatoid arthritis (Smolen 2017). In addition, mirikizumab (anti-IL-23 mAb) has been studied in participants with UC at up to 200 mg SC q4w for 40 weeks following the 12 week IV induction treatment, and was reported to be well tolerated (Geert 2019).

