1.3.1. Dose Adjustment

Participants in the randomized population with confirmed loss of clinical response (i.e., no longer satisfies the definition of clinical response as previously defined in Section 1.2) between Week M-8 and Week M-32 will be eligible to receive a single blinded dose adjustment as described below and shown in Figure 3:

[figure not shown]
- Guselkumab 200 mg SC q4w group: Participants will continue on guselkumab 200 mg SC q4w (i.e., sham dose adjustment).
- Guselkumab 100 mg SC q8w group: Participants will adjust to receive guselkumab 200 mg SC q4w.
- Placebo SC: Participants will adjust to receive guselkumab 200 mg SC q4w.

Guselkumab 24-week responders will continue to receive guselkumab 200 mg SC q4w and placebo responders at Week I-12 will continue to receive SC placebo. These participants are not eligible for a dose adjustment (they will undergo a sham dose adjustment to maintain the blind).

2771_v2

Participants who lost response will be assessed 12 weeks after the visit at which the loss of clinical response criteria are met and dose adjustment occurred. Participants who have not achieved a partial Mayo response (i.e., a decrease from induction baseline of ≥ 2 in the partial Mayo score) at 12 weeks after loss of clinical response will be discontinued from study intervention administration at that time.

Figure 3: Dose Adjustment Treatment Groups in the Maintenance Study for Participants in Clinical Response Following Induction

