5.10.1.2. PK vs Efficacy

The relationship between serum guselkumab concentrations and efficacy endpoints will be explored for the **Randomized PK Analysis Set**, e.g.:

- The relationship between serum guselkumab concentrations (quartiles) at Week M-44 and clinical response, clinical remission, symptomatic remission, endoscopic healing, histologicendoscopic mucosal healing, and endoscopic normalization, and the change in the modified Mayo score at Week M-44 will be explored. Similar PK vs efficacy analysis by ADT failure status (yes, no) may also be provided.
- Summary of change from maintenance baseline in CRP concentration (mg/L) and Fecal Calprotectin Concentration (mg/kg) at Week M-44 by serum guselkumab concentration quartiles at Week M-44 will be presented.

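### The Week M-44 exposure-response table drops dose-increased participants but keeps sham-adjusted 200 mg q4w participants still on drug, so selection into it depends on arm and outcome

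*SAP*

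**What the plan says.** SAP Section 5.10.1.1 gives its rules a wide scope: "Unless otherwise specified, the following data handling rules will apply to PK analyses". One of them reads: "For participants who received an increased dose at the time of dose adjustment, data after dose adjustment were excluded". Its only exemption is the dedicated summary of concentrations in dose-increased participants.

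SAP Section 1.3.1 shows whom the rule reaches:

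- "Guselkumab 100 mg SC q8w group: Participants will adjust to receive guselkumab 200 mg SC q4w".
- The placebo group is moved to that same higher regimen.
- For the 200 mg q4w group: "Participants will continue on guselkumab 200 mg SC q4w (i.e., sham dose adjustment".

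All three groups enter this step through confirmed loss of clinical response. Protocol Section 6.6.1 makes Week M-32 the last visit at which it can happen.

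SAP Section 5.10.1.2 then plans to explore, in the Randomized PK Analysis Set, "The relationship between serum guselkumab concentrations (quartiles) at Week M-44 and clinical response, clinical remission, symptomatic remission, endoscopic healing" and other outcomes. It claims no exemption from the data handling rules and states no intercurrent-event rule. SAP Section 4 includes placebo participants in that set if they had guselkumab in induction and a valid maintenance sample.

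**The concern.** An exposure-response table is informative only if entry to it does not depend jointly on exposure and outcome. Here it does. A participant who loses response on placebo or 100 mg q8w loses the M-44 concentration and cannot be placed in a quartile. A participant who loses response on 200 mg q4w, has the sham adjustment and remains on drug keeps the M-44 concentration and is counted. Failures leave the lower-exposure arms and stay, at least in part, in the highest-exposure arm.

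The primary estimand avoids this, because SAP Section 5.3.2 treats true and sham adjustments alike (ICE 2, composite strategy). Only the PK rule separates them. At stake is whether a reader can trust the shape of the exposure-response pattern, above all where the two guselkumab regimens meet.

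**Working it through.** **Inputs from the documents.** Planned Week M-44 remission is 25% on placebo and 45% on each guselkumab dose, with about 161 participants per arm (SAP Section 3). The planned 77% clinical response on guselkumab leaves 23% not in response, which I use as an upper scale for adjustment.

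**Assumptions.** Adjustment rates are not in the documents, so *d* is varied. Adjusted participants are taken as non-remitters (ICE 2).

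**The plan's own figure.** With a two-sided chi-square approximation, z = (0.20·√n − 1.96·√(2·0.35·0.65)) / √(0.25·0.75 + 0.45·0.55). For n = 161, z = (2.538 − 1.322)/0.660 = 1.84, so power is 96.7% (stated 97%). For n = 118 it is 90.1% (stated 90%). The planning rates are therefore read as intended. The documents give no figure for the exposure-response analysis itself.

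**Remission among retained participants.** Let *p* be true remission and *k* the share of sham-adjusted participants who discontinue before M-44 and drop out.

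- Placebo and 100 mg q8w: p/(1 − d).
- 200 mg q4w: p/(1 − k·d).

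With p = 45% on both doses:

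| Adjusted, d | 100 mg q8w | 200 mg q4w, k = 0 | k = 0.5 | k = 1 |
|---|---|---|---|---|
| 5% | 47% | 45% | 46% | 47% |
| 10% | 50% | 45% | 47% | 50% |
| 20% | 0.45/0.80 = 56% | 45% | 0.45/0.90 = 50% | 56% |
| 23% | 58% | 45% | 51% | 58% |

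If 100 mg q8w were truly worse (40% against 45%) and k = 0, it would look at least as good once 0.40/(1 − d) ≥ 0.45, that is, from d = 11.1%. Placebo at d = 40% shows 0.25/0.60 = 42%. It would pass 45% only above d = 44.4%.

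**Quartiles with placebo in the set, as written.** This simulation used 161 per arm, equal true 45% on the two doses, 40/20/20% adjusted (placebo, 100 mg q8w, 200 mg q4w), lognormal concentrations with an assumed CV of 50%, 4-fold separation of the regimens and low placebo concentrations:

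| Handling | Quartile remission, lowest to highest | Trials with lowest at or above highest |
|---|---|---|
| SAP rule, all sham-adjusted stay | 42, 56, 48, 45% | about 35% |
| SAP rule, half discontinue | 42, 55, 53, 50% | about 14% |
| All adjusted kept as failures, pre-adjustment exposure | 25, 38, 45, 45% | near 0 |

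The false peak sits in the second quartile, which is mostly 100 mg q8w. On the two guselkumab arms alone, the SAP rule gives 56, 53, 46 and 45% with all sham-adjusted staying. Keeping adjusted participants with pre-adjustment exposure gives about 45% throughout.

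**Simply lifting the exclusion.** Failures on 100 mg q8w would then carry 200 mg q4w concentrations. At 20% adjusted, the guselkumab-only quartiles become 56, 48, 38 and 38%, which is worse.

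**The case against.** The strongest reply is that the sham-adjusted are not all kept. SAP Section 1.3.1 discontinues participants without partial Mayo response 12 weeks after loss of response, and Section 5.10.1.1 drops discontinuers from by-visit analyses. This stands, and it is why the gap falls from 11 points to 6 when half discontinue and vanishes when all do. The last case is a limit: anyone adjusted at M-32 reaches the 12-week assessment at M-44 itself.

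Section 5.10.1.2 also names no intercurrent-event rule, and Section 5.5.2 extends the primary strategies only to the Section 5.5 endpoints. If observed M-44 status were used, some sham-adjusted participants could count as remitters and the bias would shrink. That also stands, and the silence itself needs filling.

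A reader might infer that the table would typically show the lowest exposure beating the highest. With placebo in the set, as Section 4 specifies, that is not the usual result under the rates assumed here. The roughly 90% frequency of such reversals arises only if the guselkumab arms are analysed alone.

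A reader might also infer that the table will decide between the regimens. The documents do not say so. Protocol Section 4.3.2 speaks of an "approximately 4-fold dose range for the dose/exposure-response assessment of maintenance therapy in the treatment of UC" as general dose justification, without naming this table. SAP Section 5.10.1.2 is exploratory, and Section 5.10.3 leaves any further exposure-response analysis to a separate plan. The randomised comparisons handle true and sham adjustment identically. The dose-increased participants' concentrations are also summarised separately in Section 5.10.1.1, although that does not repair the quartile table.

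**Conclusion.** The point holds as a defect in an exploratory analysis. Under the SAP as written, selection into the M-44 quartile table depends on both arm and outcome, and it can flatten or distort the exposure-response pattern, chiefly between the 100 mg q8w and 200 mg q4w ranges.

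The direction follows from the text; the size does not. It depends on the unknown adjustment rates, on how many sham-adjusted participants are still on drug at M-44, and on whether ICE 2 applies. With equal true remission and 20% adjusted under ICE 2, the spurious gap runs from 11 points to none. No primary or major secondary result is affected. The change should be made because the table can mislead and is cheap to correct.

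**What to change.** In SAP Section 5.10.1.2, handle true and sham dose adjustment identically in all arms, and state that the primary-estimand intercurrent-event rule applies.

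**Preferred.**

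- Keep every adjusted participant as a non-achiever.
- For exposure, use the last scheduled predose sample before the adjusted (or sham-adjusted) dose that is a trough for both guselkumab regimens: M-12, M-20 or M-28. M-36 is also a trough visit but falls after the last permitted adjustment. Use M-44 for those not adjusted.
- Do not use the flare-visit sample. For 100 mg q8w, dosed from M-4, visits such as M-8, M-16 and M-24 are mid-interval. Protocol Table 2 schedules no PK sample at M-16, M-24 or M-32, and its footnote b covers only first flares before M-32.
- Build the quartiles on the two guselkumab arms and show placebo separately.
- Report as limits the number adjusted before such a sample exists (for example at M-8) and the differing sampling weeks. Early samples may still carry induction drug, by an amount the documents do not give.

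**Minimum.** Apply the same exclusion to sham-adjusted 200 mg q4w participants and report the numbers excluded by arm. Retained rates stay inflated (56% on both doses at 20% adjusted, against a true 45%). The distortion goes only if adjustment rates are similar: at 25% and 10% adjusted, equal doses would still show 0.45/0.75 = 60% against 0.45/0.90 = 50%.

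**Cost.** SAP wording and programming. The trough samples are already scheduled in Table 2, so no new samples are needed.

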5.10.1.2. PK vs Efficacy

The relationship between serum guselkumab concentrations and efficacy endpoints will be explored for the **Randomized PK Analysis Set**, e.g.:

- The relationship between serum guselkumab concentrations (quartiles) at Week M-44 and clinical response, clinical remission, symptomatic remission, endoscopic healing, histologicendoscopic mucosal healing, and endoscopic normalization, and the change in the modified Mayo score at Week M-44 will be explored. Similar PK vs efficacy analysis by ADT failure status (yes, no) may also be provided.
- Summary of change from maintenance baseline in CRP concentration (mg/L) and Fecal Calprotectin Concentration (mg/kg) at Week M-44 by serum guselkumab concentration quartiles at Week M-44 will be presented.

5.10.1.3. Population PK Analysis

If sufficient data are available, then population PK analysis using serum concentration-time data of guselkumab will be performed using nonlinear mixed-effects modeling (NONMEM). Details will be given in a population PK analysis plan and the results of the analysis will be presented in a separate report.

5.10.2. Immunogenicity

5.10.2.1. Antibodies to Guselkumab

"Sample ADA status" and sample titer as well as the cumulative "participant ADA status" and peak titer through the visit will be coded and provided by the bioanalytical group.

Participants evaluable for immunogenicity are defined as having at least one post-dose ADA time point collected for antibodies to guselkumab detection.

The antibodies to guselkumab status (positive at any time, negative) and titers will be summarized by treatment group through Week M-44 for all participants in the following analysis sets:

- Randomized Immunogenicity Analysis Set
- Randomized Immunogenicity Analysis Set who increased their dose through Week M-44
- Randomized Immunogenicity Analysis Set who did not increase their dose through Week M-44
- Immunogenicity Analysis Set
- Continuous Guselkumab Immunogenicity Analysis Set
- Immunogenicity All Treated Analysis Set

The maximum titers of antibodies to guselkumab will be provided for participants who are positive for antibodies to guselkumab. The antibodies to guselkumab summary and analysis will be based on the observed data; therefore, no imputation of missing data will be performed.

In addition, a listing of participants who are positive for antibodies to guselkumab will be provided. The sample antibodies status, the titer, and the neutralizing antibodies status to guselkumab will be listed by visit. This listing will also provide information regarding immunomodulator status at induction baseline, dose administered, injection site reactions, adverse events temporally associated with an infusion, guselkumab serum concentration, and modified Mayo score (at applicable visits) for all visits. In addition, a list of antibodies to guselkumab status in participants who discontinued study intervention early will be provided.

5.10.2.2. Neutralized Antibodies to Guselkumab

The incidence of neutralizing antibodies (NAbs) to guselkumab will be summarized for participants who are positive for antibodies to guselkumab for all participants in the **Immunogenicity Analysis Set**, **Randomized Immunogenicity Analysis Set**, **Guselkumab Immunogenicity Analysis Set**, and **Immunogenicity Analysis Set** and have samples evaluable for Nabs to guselkumab through Week M-44.

5.10.2.3. Antibodies vs PK/Efficacy/Safety

To explore the relationship between antibodies to guselkumab status and serum guselkumab concentrations, efficacy and safety, the following analyses may be performed, if sufficient numbers of participants are positive for antibodies.

- Summary of serum guselkumab concentrations over time through Week M-44 (data following dose increase will be excluded) by antibodies to guselkumab status through Week M-44 (**Randomized Immunogenicity Analysis Set**).
- Plots of median trough serum guselkumab concentrations over time through Week M-44 (data following dose increase will be excluded) by antibodies to guselkumab status through Week M-44 (**Randomized Immunogenicity Analysis Set**).
- Summary of clinical response, clinical remission, symptomatic remission, change from maintenance baseline in modified Mayo score, endoscopic healing, histologic-endoscopic mucosal healing, and endoscopic normalization at Week M-44 by antibodies to guselkumab status through Week M-44 for the **Randomized Immunogenicity Analysis Set.**
- Summary of injection-site reactions through Week M-44 by antibodies to guselkumab status through Week M-44 for the **Randomized Immunogenicity Analysis Set.**

5.10.3. Pharmacokinetic/Pharmacodynamic Relationships

If data permit, the relationships between serum guselkumab concentration and efficacy may be analyzed graphically. If deemed feasible and necessary, exposure-response analyses may be performed. The analysis methods will be summarized in a separate analysis plan. Results of such analyses may be presented in a separate technical report.

5.10.4. Biomarkers

Changes in serum protein analytes, biopsy and whole blood RNA obtained over time will be summarized by treatment group. Associations between baseline levels and changes from baseline in select biomarkers and response to treatment will be explored. Biomarker analyses will be summarized in a separate technical report.

The biomarker analyses will characterize the effects of guselkumab concentration to identify biomarkers relevant to treatment, and to determine if these biomarkers can predict response to guselkumab. Results of serum, stool, whole blood, and mucosal biopsy analyses will be reported in separate technical reports.

5.10.5. Health Economics

Medical resource utilization, including but not limited to UC-related emergency department visits, hospitalizations, and surgeries, will be collected in this study. The WPAI-GH will also be utilized to evaluate work productivity. Analyses for medical resource utilization and health economics data are described in Section 5.5 (Other Endpoints).

5.10.6. Definition of Subgroups

The primary endpoint will be evaluated for subgroups based on demographics and baseline UC clinical disease characteristics, UC-related concomitant medication usage, and UC-related medication history all at Week 0 of the induction study, as well as maintenance stratification factors and UC clinical disease characteristics at Week 0 of the maintenance study, when the number of participants within each level of the subgroup permits.

Subgroup	Definition		
D	Demographics at Induction Baseline		
Region	 Eastern Europe: Bulgaria, Czech Republic, Hungary, Poland, Russia, Serbia, Slovakia, Ukraine, Turkey, Latvia Asia: China, Japan, Malaysia, South Korea, Taiwan Rest of World: Argentina, Australia, Austria, Belgium, Brazil, Canada, France, Germany, Ireland, Israel, Italy, Jordan, Netherlands, New Zealand, Portugal, Spain, Sweden, United Kingdom, United States 		
Baseline Age	 ≤ median Age > median Age 		
Gender	malefemale		
Race	Caucasiannon-Caucasian		
Baseline body weight	 ≤ 1st quartile > 1st quartile and ≤ 2nd quartile > 2nd quartile and ≤ 3rd quartile > 3rd quartile 		
Tobacco or nicotine use status	 non-user prior user current user 		

Subgroup Definition		
	e Characteristics at Induction Baseline	
UC disease duration	• \leq 5 years	
	• > 5 years to ≤ 15 years	
	• > 15 years	
UC disease duration	• < 2 years	
	• ≥ 2 years to ≤ 5 years	
	• > 5 years to ≤ 10 years	
	• > 10 years	
Extent of disease	• limited	
	• extensive	
Severity of UC disease	• moderate: $6 \le Mayo \text{ score } \le 10$	
	• severe: Mayo score > 10	
Severity of UC disease	 Modified Mayo score of 5 – 6 (moderate) 	
	 Modified Mayo score of 7 – 9 (severe) 	
Baseline endoscopy subscore	• moderate: subscore of 2	
	• severe: subscore of 3	
Extraintestinal manifestations	• absent	
	• present	
CRP	• $\leq 3 \text{ mg/L}$	
	• $> 3 \text{ mg/L}$	
CRP	• \leq median	
	• > median	
CRP	• \leq 1st quartile	
	• > 1st quartile and \leq 2nd quartile	
	• > 2nd quartile and \leq 3rd quartile	
	• > 3rd quartile	
Fecal calprotectin	• $\leq 250 \text{ mg/kg}$	
	• > 250 mg/kg	
Fecal calprotectin	• ≤ 1 st quartile	
	• > 1st quartile and \leq 2nd quartile	
	• > 2nd quartile and \leq 3rd quartile	
	• > 3rd quartile	
Albumin	• \leq 1st quartile	
	• > 1st quartile and \leq 2nd quartile	
	• > 2nd quartile and \leq 3rd quartile	
• > 3rd quartile		
UC-related Concomitant Medications at Induction Baseline		
Oral 5-ASA compounds	• receiving	
	• not receiving	
Oral corticosteroids including budesonide	• receiving	
and beclomethasone dipropionate	not receiving	
6-MP/AZA/MTX	• receiving	
	• not receiving	
Oral corticosteroids and 6-MP/AZA/MTX	• receiving	
	• not receiving	
Oral corticosteroids or 6-MP/AZA/MTX	• receiving	
	not receiving	

Subgroup Definition		
	cation History at Induction Baseline	
ADT failure: inadequate response or failure to tolerate advanced therapy (ADT; i.e., tumor necrosis factor alpha [TNF α] antagonists [golimumab, infliximab, adalimumab and biosimilars to these], vedolizumab, or tofacitinib)	• yes • no	
Participants with ADT failure	For participants with ADT failure to: • One ADT class	
	 Anti-TNF only 	
	 Vedolizumab only 	
	 Tofacitinib only 	
	Two ADT classes	
	 Anti-TNF and tofacitinib 	
	 Anti-TNF and vedolizumab 	
	 Vedolizumab and tofacitinib 	
	Three ADT classes	
	 Any anti-TNF and vedolizumab and tofacitinib 	
	• Two or more ADT classes	
	• Other ADT-failure combinations	
	 At least one anti-TNF (regardless of vedolizumab or tofacitinib) 	
	 Vedolizumab (regardless of anti-TNF or tofacitinib) 	
	 Tofacitinib (regardless of anti-TNF or vedolizumab) 	
	 Any anti-TNF and vedolizumab (regardless of tofacitinib) 	
	 Any anti-TNF and tofacitinib (regardless of vedolizumab) 	
	 Vedolizumab and tofacitinib (regardless of anti- TNF) 	
	 For participants with ADT failure primary nonresponse (yes) secondary nonresponse (yes) intolerance (yes) 	
	 For participants with failure to at least one anti-TNF primary nonresponse (yes) secondary nonresponse (yes) intolerance (yes) 	
	 For participants with failure to vedolizumab primary nonresponse (yes) secondary nonresponse (yes) intolerance (yes) 	

Subgroup	Definition
	For participants with failure to tofacitinib (when the number of participants within the subgroup permits) • primary nonresponse (yes) • secondary nonresponse (yes) • intolerance (yes)
Participants without ADT failure	 naïve ADT-experienced [but not documented failure]
Participants with biologic (i.e., tumor necrosis factor alpha [TNFα] antagonists and vedolizumab) failure	yesno
Participants without biologic failure	naïvebio-experienced [but not documented failure])
Colonic molecular predictive signature (MPS) status at induction baseline	Predicted endoscopic healingPredicted endoscopic non-healing
Refractory, dependent, or intolerant to oral or IV corticosteroids	 yes no
Refractory or intolerant to 6-MP/AZA	yesno
Refractory, dependent, or intolerant to oral or IV corticosteroids, but not refractory or intolerant to 6-MP/AZA	yesno
Refractory, dependent or intolerant to oral or IV corticosteroids, and refractory or intolerant to 6-MP/AZA	yesno
	sease characteristics at Week M-0
Endoscopic healing status	 yes no
CRP	 ≤ 3 mg/L > 3 mg/L ≤ median > median
Fecal calprotectin	 ≤ 250 mg/kg > 250 mg/kg
IBDQ remission	• yes • no
Fatigue response	yesno
Induction treatment	 guselkumab 400 mg IV guselkumab 200 mg IV placebo crossover to guselkumab 200 mg IV

In addition, the consistency of treatment effect for the primary and major secondary endpoints, histologic healing, histologic remission, histologic-endoscopic mucosal healing (Alternative definition 1-2), and deep histologic-endoscopic mucosal healing, will be evaluated for the following subgroups in a table summary:

Subgroup	Definition	
Induction baseline body weight	 ≤ 1st quartile > 1st quartile and ≤ 2nd quartile > 2nd quartile and ≤ 3rd quartile > 3rd quartile 	

Subgroup	Definition
CRP (at Week 0 of the induction study and the maintenance study)	• ≤ 3 mg/L • ≥ 3 mg/L • ≤ median • > median
Fecal calprotectin (at Week 0 of the induction study and the maintenance study)	 ≤ 250 mg/kg > 250 mg/kg
Fecal calprotectin (at Week 0 of the induction study and the maintenance study)	 ≤ 1st quartile > 1st quartile and ≤ 2nd quartile > 2nd quartile and ≤ 3rd quartile > 3rd quartile
ADT failure profile	 ADT-naïve ADT-experienced but not failed ADT-non failure ADT-Failure
Biologic failure profile	 Biologic-naïve Biologic-experienced without documented failure [i.e., discontinued biologic therapy for other reasons] Biologic-non failure Biologic-failure
Colonic molecular predictive signature (MPS) status at induction baseline	Predicted endoscopic healingPredicted endoscopic non-healing
Induction treatment	 guselkumab 400 mg IV guselkumab 200 mg IV placebo crossover to guselkumab 200 mg IV

